#### **5.- Proposal from the researchers to ensure compliance with legal and ethical aspects of the research and the rights of the participants**

In this study, clinical research is carried out with health products on people.

In order to safeguard the integrity, well-being and right to privacy of the participating subjects, the study is carried out following the standards dictated by the Declaration of Helsinki of the World Medical Assembly (64th General Assembly, Fortaleza, Brazil, October 2013). , the Council of Europe Convention on human rights and biomedicine, the Standards of Good Clinical Practice, Royal Decree 1090/2015, of December 4, which regulates clinical trials with medicines, the Ethics Committees of Research with medicines and the Spanish Registry of Clinical Studies and Royal Decree 1591/2009, of October 16, which regulates health products.

Before the beginning of the study, explicit informed consent will be requested from participants, through an online form in which the objectives and what their participation consists of will be explained (Annex 1).

Compliance with Organic Law 3/2018, of December 5, on the Protection of Personal Data and guarantee of digital rights, will be ensured.

The privacy of the participants will be protected and the exclusive use of the data collected for the purposes of the project and those studies that may result from it will be guaranteed.

#### **6.- Determination of the potential benefits and risks of the study**

The participation of the subjects in this project implies the eventual possibility of suffering adverse effects, none of which seriously compromise the integrity of the subject. Every effort will be made to remain alert to potential complications and unexpected results. If complications occur, the first concern will be patient safety.

The intensive use of FES can entail a series of risks (described below) that will be minimized by taking their respective precautionary measures:

- Electrical stimulation may cause an uncomfortable sensation or very mild pain in the first few uses until you become familiar with the sensation.
- It is normal for the area where the stimulation has been applied to appear red after removing the device; this redness should disappear in approximately one hour.
- In some cases, electrical stimulation or contact of the gel with the skin could cause an allergic reaction or irritation at the contact surface.

The patient must immediately stop using the device in the following cases:

- There is redness or irritation in the stimulation application area during more than one hour after removing the electrode.
- Presents blisters or sores in the stimulation application area.
- You feel a significant increase in muscle spasticity.
- You feel cardiac stress or tachycardia during pacing.
- Presents swelling in the extremity.

Regarding the collection of data on motor function, this is carried out using non-invasive techniques so they do not pose any risk to the participant.

The benefits that the subject obtains in this project are the motor improvement and functionality of the upper limb, as well as a direct contribution to the advancement of knowledge of new techniques or therapies for their pathology.

#### **7.- Information and informed consent document, if applicable**

All participants will be sent an information document and a informed consent, where the entire study that is going to be carried out and what data will be used will be explained to them. It is attached as annex 1.

#### **8.- Compensation provisions for participants, if applicable**

Not applicable.

#### **9.- Coverage in case of damage due to participation, if applicable**

The device is sufficiently safe, the sample corresponds to healthy subjects, and no

contemplates the possibility of generating any type of damage.

#### 10.- Description of the data analysis and the statistical study required, if applicable

The characteristics between groups will be analyzed before the start to confirm that there are no differences between them before the start of the intervention.

Subsequently, intra-group analysis will be done to see the effects on each of them, as well as inter-group analysis to see if there are differences between the different interventions. These intra-group and inter-group analyzes will be done with respect to the baseline and follow-up measurement.

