The Fesia Grasp system is a FES-based neurological hand rehabilitation device developed by Fesia Technology (Donostia-San Sebastián, Spain). This is a commercial device designed for manual dexterity rehabilitation, which delivers a train of biphasic pulses of different widths and amplitudes to different electrode fields asynchronously, meaning that different electrode fields are activated with an interval predefined between pulses Malešević et al (2017).

Fesia Grasp, generates superficial electrical stimulation of the forearm muscles to trigger eight different flexion and extension movements of the wrist and fingers in order to restore the function, freedom and independence of the patient's hand after a stroke, Martin -Odriozola et al (2021).

The study aims to answer the PICO research question:

Q: healthy adults

I: FES and, multfield FES.

C: video games

O: Motor imagination, strength, manual dexterity.

The aim is to compare different tools in a population sector to check if there is an improvement in motor skills through the use of FES.

2.- Objectives

General objective:
 
 
• Check the effects of FES and virtual reality regarding motor imagination, strength and manual dexterity.
 
 
Secondary objectives:
 
 
• Find out if functional electrical stimulation improves motor imagination, both kinesthetic and visual, as well as manual dexterity and strength.
 
• Find out if an intervention based on the use of virtual reality improves motor imagination, both kinesthetic and visual, as well as manual dexterity.
 
• Check if there are differences between FES, multi-field FES, and virtual reality in terms of visual motor imagination, kinesthetic and manual dexterity.
 

3.- Project description

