
The present work is a clinical, randomized study of parallel groups of a quasi-experimental type.
 
A sample of university students will be divided into 4 groups, where one of them will act as a control group (without intervention), and the other three will perform hand training with two different types of FES devices (conventional and multi-field). and a last group will receive hands-on training with video games.
 
Intergroup analyzes will be performed before the start of training (pre-intervention), after finishing the program (post-intervention), and three weeks after finishing (follow-up evaluation). Likewise, intragroup analyzes will be carried out to check whether the training has caused an improvement in the quality of motor imagination, as well as an improvement in manual dexterity in each of the groups.
 
To carry out the project, a collaboration agreement will be signed with the company FESIA TECHNOLOGY SL, which will provide a FESIA GRASP device for the study, as well as the consumables (electrodes) necessary for the development of the study. The agreement is currently being evaluated by the UBU legal office.
 
It is planned to register the study on the international platform Clinicaltrials.gov.

4.- Material and methods

4.1 Type of study
 
Controlled, randomized, parallel group clinical trial. Unicentric, and with blind evaluation by third parties. Quasi-experimental.
 
4.2. Description of devices
 
Four parallel groups are planned. A first group that will have an intervention based on multi-field FES with the FESIA GRASP device; another group that will receive only FES

with the Globus Elite electrostimulation device (device with conventional electrodes); a third group that will receive an intervention based on virtual reality; and finally a control group, which will not receive any treatment.

The three devices are described below.

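### No outcome, visit or between-group contrast is primary and no error control is stated, so a positive conclusion could rest on any of many tests

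*Combined protocol and SAP*

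**What the plan says.** The general objective in section 2 is to "Check the effects of FES and virtual reality regarding motor imagination, strength and manual dexterity", which gives three domains equal rank. Section 4.5 measures them with six variables: Nine Hole Peg Test time, Box and Block count, grip strength, the chronometric ratio, and the MIQ-RS visual and kinesthetic subscales.

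Section 3 sets up four groups, one of them an untreated control. It plans between-group analyses before training, after training and at follow-up, plus within-group analyses. Section 10 is the whole statistical plan. After a baseline comparison, it says "intra-group analysis will be done to see the effects on each of them" and adds "inter-group analysis to see if there are differences between the different interventions". It then says "These intra-group and inter-group analyzes will be done with respect to the baseline and follow-up measurement", which does not name the post-intervention visit.

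The only objective that spells out a between-group comparison is the third secondary one: "Check if there are differences between FES, multi-field FES, and virtual reality in terms of visual motor imagination, kinesthetic and manual dexterity". It leaves out the control group and strength. The PICO statement in section 1 gives video games as the comparator.

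Nothing in the text available for review states a significance level, a test or model, an omnibus gate, an adjustment, or which result answers the research question.

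**The concern.** When nothing is primary, the decisive comparison can be chosen after the results are known. A statement that conventional FES, multi-field FES or video games improve imagery, dexterity or strength could then come from any outcome, at either post-baseline visit, between any pair of groups, or from a within-group change. Each such result would carry a nominal p-value that overstates the evidence. This cannot be repaired after the data have been seen, so it is more than a missing detail.

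The sections also support different test sets. Section 3 does not restrict the groups compared, section 2 lists only the three active ones, and section 10 names only baseline and follow-up. Two analysts following the plan could reach different conclusions from the same data.

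**Working it through.** The plan states no error rate, so there is no figure of its own to reproduce.

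**Inputs from the documents**
- Outcomes: 6 (section 4.5), or 5 if strength is left out as in the third secondary objective.
- Groups: 4, giving 4 × 3 / 2 = 6 pairs; or the 3 active groups, giving 3 pairs.
- Post-baseline visits: 2 (section 3), or 1 if only follow-up is compared with baseline (section 10).
- Size: 20-25 per group (section 4.3.2).

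**Assumptions, not in the documents**
- Two-sided 0.05 per test and no true differences.
- Normal data and 22 per group.
- Correlation between visits 0.5-0.7, and between outcomes 0-0.7 unless noted.

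**Number of tests and independence benchmark.** With k independent tests, the chance of at least one false positive is 1 − 0.95^k.
- k = 6 × 6 × 2 = 72: 1 − 0.95^72 = 0.975; expected false positives 72 × 0.05 = 3.6.
- k = 5 × 3 × 1 = 15: 1 − 0.95^15 = 0.54; expected 0.75.
- k = 6 × 2 = 12 omnibus tests: 1 − 0.95^12 = 0.46; expected 0.6.

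**Allowing for dependence.** Pairs share groups, visits share participants and outcomes may be correlated, so the independence figures are too high. Simulation under no effect gives:

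| Reading | Tests | Chance of at least one false positive |
|---|---|---|
| All pairs, 6 outcomes, 2 visits | 72 | 0.71-0.91 |
| All pairs, 6 outcomes, 1 visit | 36 | 0.62-0.75 (outcome correlation 0-0.5) |
| 3 active groups, 5 outcomes, 2 visits | 30 | 0.62-0.70 (outcome correlation 0-0.5) |
| 3 active groups, 5 outcomes, 1 visit | 15 | 0.32-0.48 |
| One omnibus F test per outcome and visit, 4 groups | 12 | 0.27-0.45 |
| Omnibus F test, 3 active groups, 5 outcomes, 1 visit | 5 | 0.19-0.23 (outcome correlation 0-0.5) |

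Using the omnibus test as a gate before pairwise tests gives the same simulated chance as the omnibus tests alone.

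**One outcome, one visit, three contrasts with control.** Unadjusted, the chance is about 0.12. With Bonferroni it is about 0.04-0.05.

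**Detectable difference at 80% power.** By the normal approximation, d = (z for alpha/2 + z for power) × √(2/n).
- At 0.05: (1.960 + 0.842) × √(2/20) = 0.89 and × √(2/25) = 0.79. The noncentral t gives 0.91 and 0.81.
- At 0.05/3: (2.394 + 0.842) × √(2/20) = 1.02 and × √(2/25) = 0.92. The noncentral t gives 1.06 and 0.94.

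**The case against.** The strongest reply is that the plan never commits to testing every pair on every outcome at every visit. The explicit between-group objective is narrower, and the wording in section 10 fits one omnibus test per outcome and visit as well as it fits pairwise tests. This stands. It is why no single error rate can be attributed to the plan, and why the omnibus readings come out well below the pairwise ones.

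A reader might infer that a false positive is close to certain. The documents do not support that. The 97.5% figure needs 72 independent tests, which the design rules out, and the 72 tests are themselves only one reading.

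A reader might also add 6 × 2 × 4 = 48 within-group tests and speak of 120 chances for a false positive. That does not hold either. People may perform better on repeated tests through practice, so a significant within-group change may be real. The problem with such a change is attribution: it cannot show that an intervention works.

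What the reply does not remove is the absence of a primary comparison. Every reading tried gives an error rate far above 5%.

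**Conclusion.** The concern holds in this form: there is no primary outcome, visit or contrast and no stated error control, so any of many tests could carry the conclusion. The chance of at least one false positive between-group result is roughly 70-90% for all unadjusted pairs on six outcomes at two visits. It is about 30-50% for the three active groups on five outcomes at one visit, and about 27-45% for omnibus tests in four groups at two visits. These figures rest on an assumed 0.05 level, no true effects, about 22 per group and assumed correlations. The absence of a primary comparison rests on the text alone. The point should be settled before the analysis; it does not mean that the design is unusable.

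**What to change.** In section 10, before anyone sees outcome data by group:

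1. Name one primary outcome, one visit and one family of between-group contrasts.
2. Control that family at two-sided 0.05, with Dunnett for active versus control or Holm for any other set.
3. Report all other outcomes, visits and contrasts as secondary or exploratory, with 95% confidence intervals.
4. State that within-group changes are descriptive and will not be used to claim that an intervention works.

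Motor imagery at the post-intervention visit is a reasonable candidate. Imagery is the research question in section 1, and the follow-up time is inconsistent: three weeks in section 3, two weeks in section 4.4.2. Those sections must be reconciled in any case.

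Two choices belong to the sponsor. One is between MIQ-RS and chronometry, bearing in mind that section 4.5 says imagery assessment needs at least two tests; if both are made primary, the adjustment must cover both. The other is between active versus control and the active-versus-active comparison in section 2.

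The change costs a paragraph and some power. With three primary contrasts and Bonferroni, the detectable difference rises from 0.81 to 0.94 SD with 25 per group, and from 0.91 to 1.06 SD with 20. Dunnett costs slightly less. Adjusting across all 72 tests instead (0.05/72 = 0.0007 each) would cost far more: by the normal approximation, from 0.79-0.89 SD to 1.20-1.34 SD. A small primary family is therefore the workable choice.

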Adults. University students.

**12.4.- Indicate how the data will be collected (interviews, surveys, forms, Internet, etc.).**

The data will be collected through a clinical interview and the administration of the tests in person.

**12.5.- Indicate whether the data are going to be anonymized (it is not possible to identify the persons) or pseudo-anonymized (a non-identifying or identifiable code is assigned to each subject, so that subsequent identification would be possible).**

The data will be pseudonymised. A non-identifying, non-identifiable code is assigned to each subject, so that subsequent identification would be possible.

**12.6.- In case of anonymization or pseudonymization, indicate the techniques used.**

The data will be dissociated to the extent possible.

- The researchers will only have access to the personal data of the participants in the informed consent document. The signed document will be a paper file, which will be kept in a locked cabinet within the UBU facilities.
- Once the project has started, only the main researcher will have access to the identifying data of the participants.
- The data collected in the interviews and test administration will be transferred to an Excel document, to which only the project researchers will have access.
- Data from the pre/post intervention and follow-up interviews will be included in Excel, where each participant will be assigned an anonymous participation code that allows the linking of pre-post intervention and follow-up results.
- The anonymous participation code will not allow the identification of participants: It will be composed of the first letter of the first name and the last of the surnames. This will be followed by a hyphen and the figure resulting from adding the day and month of data collection. For example, if the interviewer's name is [name], and she conducted the interview on May 12, her code will be: MAZ-17

**12.7.- If applicable, indicate if several organizations or partners participate in the project.**

A collaboration agreement will be signed with the company FESIA TECHNOLOGY SL, for the transfer of the FESIA GRASP device.

**12.8.- Duration of data processing. Period of conservation/deletion of data at the conclusion of the investigation and place of conservation.**

The databases will be kept throughout the life of the project and at least during the three subsequent years in order to ensure the processing of data for exclusive purposes research. The storage location for the information will be One Drive (package of Office 365) from the University of Burgos; Therefore, the information will be hosted in the servers of said University.

**12.9.- Indicate if the purpose of the treatment is:**

Create personal profiles.

Process data on a large scale.

Treat special categories of data.

**Monitoring, control and observation of people (monitoring).**

Use technologies that may be especially intrusive, electronic surveillance, data mining, biometrics, genetic techniques, geolocation.

You process data related to the observation of public access areas.

**12.10.- Is the international transfer of data outside the European Union foreseen?**

No.

**12.11.- Will data be communicated or transferred to third parties?**

If a scientific publication were derived from the work carried out, the database (without the possibility of identifying the subject) would be shared in open access databases, in addition to presenting the possible results in the content of the article.

**12.12.- Is the reuse of personal data for research purposes planned?**

No. It is not planned to contact the subjects again once this project ends.

**12.13.- Briefly indicate the technical and organizational measures that will be taken with respect to data processing (pseudonymization, access control and registration, data encryption or coding...).**

Some of these measures have already been mentioned in previous sections. Next, they appear again collected:

- Each participant will be given a non-identifiable code, with the following

formula: The anonymous participation code will not allow the identification of the

participants: it will be composed of the first letter of the first name and the last of the

surnames. This will be followed by a dash and the figure resulting from adding the day and month

from the day of signing the informed consent. For example, if your name is [name], and you conducted the interview on May 12, your code will be: MAZ-17

**UNIVERSIDAD  
DE BURGOS**

**A/A of the President of the Commission  
Bioethics of the University of Burgos**

- Informed consents, where identifying data appear, are  
They will be kept under lock and key, in paper format, in the facilities of the Faculty of Health Sciences, and only the principal investigator will have access.
- Digital files derived from research, such as databases and others will be hosted on the OneDrive Platform (Office 365), with limited access to project researchers.

**12.14.- Indicate other aspects that you consider relevant regarding data protection.**

Participation will be free and there will be no type of benefit to participants.

Contact information for the person responsible will be provided to clarify any doubts that may arise regarding the process.

